
6.1.10 TEWL and Tape Strips

TEWL will be performed at the biopsy and skin swab sites (nondominant arm and upper buttocks) to assess the skin barrier at visits 2-12. Tape strips will be also be obtained from ichthyosis subjects at baseline and weeks 8, 16, 32 and 52. Tape strips are purchased from CuDerm. Tape stripping will be performed on the dominant upper outer arm (same sites serially) using circular 2x2 or 3x3 cm transparent tape strips at lesional skin sites for each patient or unaffected skin site for controls. The tape strips will be used for detection of alterations of epidermal lipids and proteins in the outer stratum corneum of epidermis. We will be sending tape strips for proteomics and lipidomics analysis to the laboratories at Mt. Sinai/Rockefeller University medical center under the supervision of [name] and other designated laboratories. Alternating tape strips will be obtained for these analyses. Equal pressure will be applied to affected areas for 10 seconds. Up to 32 tape strips will be serially extracted on skin sites. Tape stripping is painless and, in our experience and that of the literature, has no adverse sequelae.

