Tape strips (noninvasive) will be taken at baseline, Week 8, Week 16 or Early Termination visit, Week 32, and Week 52 for lipidomic and proteomic assessments of the outer epidermis from the dominant arm (opposite to the nondominant arm used for TEWL, microbiome and biopsy measurements) at a site the clinically appears similar. A buccal swab will be collected and banked for future pharmacogenomics studies. Given our goal of determining whether the increases in skin Th17 cytokines reflect only a response to the barrier defect (for their antimicrobial effect) vs. pathogenic in driving inflammation – as

Product: Secukinumab

Protocol Number: CAIN457AUS05T

Date: 14 July 2018

19

well as to gauge alterations in microbial organisms as Th17 activation is suppressed by treatment, we will capture swabs for future microbiome assessment. Swabs for bacteria and fungi (including candida) will be obtained from the forehead, buttock and outer arm (near the biopsy site) at each visit, beginning at baseline. In flow studies of activated lymphocytes from patients with ichthyosis, we have recently found increases in blood levels of IL-22 cytokine, providing evidence of systemic activation of the IL-23/Th17 pathway. As a result, at baseline, Week 8, Week 16 or Early Termination visit, Week 32, and Week 52 we will also evaluate fasting lipids, glucose and CRP (as well as measure waist circumference) to assess for metabolic abnormalities.

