5.6.2 Instructions for prescribing and taking study treatment

Throughout the study, treatment (either secukinumab or placebo) will be administered subcutaneously either by the subject or by an approved individual. Prefilled syringes will be provided by the site staff to the subject. Initial injections will be performed at the site to train subjects in proper subcutaneous injection technique. Study personnel will perform first injection with subject observing, then subjects will use the second syringe to demonstrate the ability to inject themselves. After this instruction and observation, subjects will be able to self-administer weekly or monthly injections.

We will contact subjects weekly by phone/Skype/FaceTime (subjects will designate which is best) on weeks 1-3 to answer questions, assure adherence to administration, and ensure safety and return at week 4. Subjects will keep a diary of administration dates and times, which will be reviewed at each appointment. All subjects who receive at least one dosage will be counted in the ITT population.

Injections are to be administered at a different anatomic location (such as dominant upper arm, thigh, or any quadrant of the abdomen except for 2 inches around the navel area) than the previous injection. Subjects may not self-inject upper outer arm but this area may be used by caregiver or healthcare provider for injection. Injections should not be given in areas where the skin is tender, bruised, erythematous, or indurated if possible.

Product: Secukinumab

Protocol Number: CAIN457AUS05T

Date: 14 July 2018

24

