5.6.3 Prohibited treatment

Subjects should not receive live vaccines during this study. They may not use any topical agent for the treatment of ichthyosis other than over the counter emollients. They may not be on any systemic agents for the treatment of ichthyosis. Subjects who experience skin infection requiring antibiotics during the study will not be discontinued from study drug or withdrawn from the study. The therapies they require will be noted by investigator on the case report form.

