6.1.12 Skin Swabs and Scrapings for Microbiome (Appendix 12)

Skin swabs and scrapings will be collected at visits 1-12. Subjects will be instructed to not bathe, shower, or apply any topical product to the area that will be tested 24 hrs before the visit. Vigorous activity will also be minimized for several hours prior to swab. A questionnaire will be administered along with swabs. Swabs and scrapings will be collected from the nondominant side at upper outer arm (at biopsy and TEWL site), upper buttock, and scalp. Swabs will be labeled with the subject's study ID, study visit number, and visit date.

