6.2.4 Skin Biopsy

Skin biopsies will be obtained from the non-dominant upper outer arm and will occur during the baseline visit, visit 6 (week 16), visit 9 (week 32), and visit 12 (week 52) as indicated in Appendix 1. Subjects will be instructed to not bathe, shower, or apply any topical product to the area that will be biopsied 24hrs before the visit. The area will be marked and then cleaned with an antiseptic wash. A 4.5 mm punch biopsy will be obtained and bisected for immunohistologic and qRT-PCR studies. The defect will be closed with a suture and dressed with a self-adherent compression dressing. The subject will be provided with instructions for wound care and suture removal.

Product: Secukinumab

Protocol Number: CAIN457AUS05T

Date: 14 July 2018

29

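### Tape strips for lipid analysis come from the dominant arm, which no 24-hour product-free instruction covers, so emollient applied on the visit day can contaminate the lipid readout

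*Combined protocol and SAP*

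**What the plan says.** **Site and purpose.** Section 6.1.10 states: "Tape stripping will be performed on the dominant upper outer arm (same sites serially"). Section 3.5 shows that the choice of arm is deliberate, since strips come "from the dominant arm (opposite to the nondominant arm used for TEWL, microbiome and biopsy measurements"). On purpose, section 6.1.10 says: "The tape strips will be used for detection of alterations of epidermal lipids and proteins in the outer stratum corneum of epidermis". On timing: "Tape strips will be also be obtained from ichthyosis subjects at baseline and weeks 8, 16, 32 and 52". The schedule in Appendix 1 agrees.

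**Product-free provisions.** There are three, each limited to a site:
- Section 6.1.12 bars bathing and topical products on the tested area for 24 hours. It defines the sites thus: "Swabs and scrapings will be collected from the nondominant side at upper outer arm", with upper buttock and scalp added.
- Section 6.2.4 tells patients not to bathe or "apply any topical product to the area that will be biopsied 24hrs before the visit". That biopsy site is the nondominant upper outer arm.
- The exclusion criterion in section 4.2 concerns emollient on the area to be biopsied.

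**Emollients in general.** Section 5.6.3 says: "They may not use any topical agent for the treatment of ichthyosis other than over the counter emollients". Section 3.1 adds that the placebo condition restricts neither bathing nor emollients.

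**Records.** The diary (sections 5.2.1 and 5.2.2) includes emollient and bath use. The microbiome survey asks for products by brand and how often they are used. Its 24-hour question is confined to swabbed areas.

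**The concern.** The strips are meant to show changes in lipids and proteins of the outer stratum corneum, which is also where a topical product lies. Section 1.1 describes emollients as part of most patients' routine care, and during the trial they are the only topical ichthyosis treatment allowed. A patient who follows every written instruction may still arrive with fresh emollient on the arm to be stripped. Part of the measured lipid profile would then come from the product.

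Section 3.5, where the strips are introduced, has the identification of treatment response biomarkers among its aims, in line with secondary objective 4. A lipid shift caused by changed emollient habits could be mistaken for such a biomarker. Contamination of a collected strip cannot be undone afterwards.

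**Working it through.** The plan states no figure on this point, so the check sets its provisions side by side.

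| Skin sample or measurement | Site | 24-hour product-free instruction |
|---|---|---|
| Swabs and scrapings (6.1.12) | Nondominant upper outer arm, upper buttock, scalp | Yes, in 6.1.12 |
| Biopsy (6.2.4) | Nondominant upper outer arm | Yes, in 6.2.4; also the 4.2 criterion |
| TEWL (6.1.10) | Biopsy and swab sites | Yes, because the sites are shared |
| Tape strips (3.5, 6.1.10) | Dominant upper outer arm | None |

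None of the three provisions reaches the tape-strip site, and section 6.1.10 has no washout, cleaning or discard-first-strips step.

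**Occasions exposed.** 40 patients (section 9.5) × 5 time points = at most 200 sampling occasions. The share with product on the arm is not given.

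**Where a bias between arms could arise.** As a simple additive picture, let q be the share of patients in an arm with product at the tape site, and c the average signal the product adds. Then

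measured difference = true difference + (q on secukinumab − q on placebo) × c.

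- *Baseline:* randomisation makes the two shares equal in expectation, so contamination adds noise but no expected difference.
- *Weeks 8 and 16:* a placebo comparison exists, and emollient use may by then have changed with response, so the bracket need not be zero. This covers at most 40 × 2 = 80 occasions, 20 patients per arm.
- *Weeks 32 and 52:* everyone receives secukinumab from week 16 (section 3.4.3), so there is no placebo contrast to bias. Individual readings, and changes from baseline, can still be contaminated.

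The documents supply neither q nor c, so the extra term cannot be sized.

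**Could the records repair it?** The diary and survey give product identity and frequency. Neither asks for body site, and the one question about the last 24 hours omits the tape-strip arm. Use at that site before sampling is therefore not captured.

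**The case against.** **The instruction on the tested area might include the tape site.** It stands in the swab section, which lists nondominant-side sites, and section 3.5 sets the tape-strip arm apart from them. A whole-body reading of the bathing ban would not help: it removes no product from the dominant arm and could leave earlier applications unwashed.

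**Up to 32 serial strips go below the surface.** This may reduce the problem. But alternating strips go to the analyses and no early ones are set aside, so it does not remove the problem.

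**Site preparation may be in the institutional procedures cited in section 6.4.1.** That is possible. A general reference does not show that this site is covered, and the protocol itself states product-free rules for the other sites.

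**The assessment is supportive.** This stands. Tape strips are listed under other assessments, are not a named endpoint in sections 2.1 to 2.4, and have no analysis in section 9.

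**Stronger readings a reader might infer.** Three are not supported:
- *That emollient use goes unrecorded.* The diary and survey do record it; only site-specific use in the last 24 hours is missing.
- *That the comparison with placebo is biased at all five time points.* It can be biased only at weeks 8 and 16.
- *That section 5.6.2 makes the tape site an ordinary injection site,* because it lists places "such as dominant upper arm, thigh, or any quadrant of the abdomen". The same section bars self-injection of the upper outer arm and leaves it to caregivers or providers. The matter is also unrelated to emollient contamination.

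**Conclusion.** The gap is real. The product-free provisions leave out the one sampled skin site whose assay measures lipids, in patients free to use emollients there. Contamination is possible on up to 200 occasions; a bias against placebo is possible only on the up to 80 at weeks 8 and 16. Its size and direction are unknown.

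The conclusion assumes that some patients apply emollient to the dominant arm shortly before a visit and that some of it reaches the analysed strips. A between-arm bias needs the further assumption that such use comes to differ by treatment, which is plausible if responders apply less but is shown nowhere in the documents. The case made here is for the lipid readout; the documents give no basis for saying how far the protein readout is affected. The IASI primary analysis and the primary safety endpoint do not depend on these strips. The point is worth correcting because the correction is cheap.

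**What to change.** 1. In section 6.1.10, extend the existing 24-hour instruction (no bathing or topical product on the area) to the tape-strip site on the dominant upper outer arm before the baseline and week 8, 16, 32 and 52 visits.
2. In the microbiome survey, widen the 24-hour product question from swabbed areas to swabbed and tape-stripped areas.
3. Keep every sample in the main lipidomic analysis, and use the resulting flag only for a sensitivity analysis. Dropping flagged samples from the main analysis would select on behaviour after randomisation that may itself follow response, in a trial of 40.

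**Cost.** One sentence, a small change to one questionnaire item, and one sensitivity analysis. Patients leave one more small area without emollient for 24 hours, five times. Swabs are taken at all of these visits, so they already follow the same instruction at other sites.

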6.1.11 Photography (Appendix 11)

Photography will be done at study visits 1-12 as indicated in Appendix 1. Photos will be labeled using subject's study ID as well as subject visit number and date of the photo. Photos will be uploaded to a

Product: Secukinumab

Protocol Number: CAIN457AUS05T

Date: 14 July 2018

28

secure, password-locked file per institutional Data security Plan and deleted from the camera memory card as soon as possible.

6.1.12 Skin Swabs and Scrapings for Microbiome (Appendix 12)

Skin swabs and scrapings will be collected at visits 1-12. Subjects will be instructed to not bathe, shower, or apply any topical product to the area that will be tested 24 hrs before the visit. Vigorous activity will also be minimized for several hours prior to swab. A questionnaire will be administered along with swabs. Swabs and scrapings will be collected from the nondominant side at upper outer arm (at biopsy and TEWL site), upper buttock, and scalp. Swabs will be labeled with the subject's study ID, study visit number, and visit date.

6.2 Data Collection at Subsequent Study Visits

Study visits including baseline visit [day 0] and visits 1-12 will occur at one of the study sites (Appendix 1)

6.2.1 Complete Skin Examination

A targeted exam (necessary components determined by PI or qualified study staff) will occur at visits 2-12 as indicated in Appendix 1. Additional exam components and maneuvers may be necessary depending on presenting symptomatology and are at the discretion of the PI or study staff. If exam findings occur after the informed consent form has been signed and meet the criteria for an AE, they will be documented as such in the subject's file.

6.2.2 Blood Samples for Biomarkers

A blood sample will be collected at screening (if on a systemic retinoid) and visits 2, 4, 6, 9, and 12 as indicated in Appendix 1 for biomarkers and RNA analysis. A blood draw by a licensed phlebotomist will be collected by study staff. Serum samples will be labeled with the subject's study ID, study visit number, and visit date and stored at -80°C until analysis for cytokines is performed.

6.2.3 DLQI and iQoL-32 (Appendices 7,8)

DLQI and iQoL-32 will be obtained at the baseline visit, Visit 4 (week 8), visit 6 (week 16), visit 9 (week 32), and visit 12 (week 52) as indicated in Appendix 1. DLQI is the most commonly used and first dermatology-specific quality of life assessment tool (Basra et al 2008). It can be used to assess various dermatologic conditions and has been a reliable measure of quality of life (Finlay 1994). IqoL-32 is a validated, 32-item quality of life questionnaire that is specific to ichthyosis and has been shown to be highly correlated to clinical severity (Dreyfus et al 2013).

6.2.4 Skin Biopsy

Skin biopsies will be obtained from the non-dominant upper outer arm and will occur during the baseline visit, visit 6 (week 16), visit 9 (week 32), and visit 12 (week 52) as indicated in Appendix 1. Subjects will be instructed to not bathe, shower, or apply any topical product to the area that will be biopsied 24hrs before the visit. The area will be marked and then cleaned with an antiseptic wash. A 4.5 mm punch biopsy will be obtained and bisected for immunohistologic and qRT-PCR studies. The defect will be closed with a suture and dressed with a self-adherent compression dressing. The subject will be provided with instructions for wound care and suture removal.

Product: Secukinumab

Protocol Number: CAIN457AUS05T

Date: 14 July 2018

29

6.2.5 Adverse Event Assessment

Adverse event assessments will occur at visits 1-12. Additionally, subjects will be queried by study coordinator about tolerability and any adverse events during the weekly phone or Skype sessions during weeks 1-3 of the study. Adverse event definitions are detailed in section 7.

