1.6 Risks and Benefits of Secukinumab

Previous studies using secukinumab have found the following risks associated with treatment:

- **Infections:** In clinical trials, a higher rate of infections was observed in subjects treated with secukinumab (31%) compared to placebo (18%). In trials for moderate-severe plaque psoriasis, psoriatic arthritis, and ankylosing spondylitis, higher rates of common infections such as nasopharyngitis (11.4% versus 8.6%), upper respiratory tract infection (2.5% versus 0.7%) and mucocutaneous infections with candida (1.2% versus 0.3%) were observed with secukinumab compared with placebo. Given that individuals with ichthyosis have an increased risk of staphylococcal and fungal/candidal infections of the skin, there is a possibility that there may be more skin infections (beyond the known increase in mucosal candida infections), which will require vigilance.
- **Inflammatory Bowel Disease:** Both exacerbations and new onset cases of this condition occurred in patients treated with secukinumab in trials for plaque psoriasis, psoriatic arthritis and ankylosing spondylitis
- **Hypersensitivity Reactions:** Anaphylaxis and cases of rash or urticaria occurred in secukinumab treated patients in clinical trials. The removable cap of the COSENTYX Sensoready pen and the COSENTYX prefilled syringe contains natural rubber latex which may cause an allergic reaction in latex-sensitive individuals (Novartis Full Prescribing Information 2016)
- Pharyngitis, fatigue and peripheral edema were noted more in subjects receiving 3 doses of secukinumab when compared to subjects receiving 1 or 2 doses (Papp et al 2013)
- Mild to moderate (Grade 1 or 2) neutropenia was noted in 12.1% of patients receiving regular s.c. injections of secukinumab. However, there were no AEs resulting from this neutropenia and no subjects were discontinued from treatment because of this (Rich et al 2013)
- IL-17A blockade does not appear to interfere with protective antibody levels after vaccinations such as the meningococcal vaccine or the influenza vaccine (Chioato et al 2012) when comparing antibody levels in individuals who had received secukinumab s.c. to those who did not.
- Currently, there is no evidence that secukinumab imparts an increased risk of malignancy

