3.4.3 Cross-Over Phase-Phase 2 (Week 16 -- Week 19)

At Week 16, all subjects will be eligible to crossover into the second phase of the study, in which all subjects will receive secukinumab (300 mg). In order to maintain the initial blind and complete 4 months of treatment, subjects who had been randomized to secukinumab in the double blind phase will continue to receive secukinumab at a dose of 300 mg s.c. at Week 16. However, they will also receive three placebo injections at Weeks 17, 18, and 19, so that neither the subject nor the assessor knows if the subject had received secukinumab or placebo in the double blind phase. Subjects, who had been randomized to placebo in the double blind phase, will receive four doses of secukinumab at a dose of 300 mg s.c. at Week 16 to be administered on week 16, 17, 18, and 19 for loading. Weeks 16 will be administered by the subject (or a doctor) in clinic during study visits. Weeks 17, 18, and 19 will be administered by the subject (or a caregiver) at home. At Week 16, the primary endpoint will be assessed. Complete Metabolic Panel, and CBC at will be assessed at Week 16.

Product: Secukinumab

Protocol Number: CAIN457AUS05T

Date: 14 July 2018

18

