5.2.1 Double-Blind Phase: Secukinumab arm

Subjects who meet eligibility criteria and have a normal baseline physical examination and laboratory testing will be enrolled in the double-blind phase. Each subject will receive 300 mg s.c. of secukinumab (administered in two pre-filled syringes) at Baseline (Day 0), Weeks 1, 2, 3, 4, 8, and 12.

Injections will be performed at the site for the initial visit to train subjects in proper aseptic and subcutaneous injection technique (per Novartis Package Insert 2016). Subjects will use the second syringe to demonstrate the ability to inject themselves. After this baseline instruction and observation of injection technique, subjects will be able to self-administer weekly or monthly injections.

We will contact subjects weekly by phone/Skype/FaceTime (subject will designate which is best) on weeks 1-3 to answer questions, assess compliance with administration, including proper disinfection of subject's hands and administration site, as well as to ensure safety and return at week 4. Subjects will keep a diary of administration dates and times (as well as use of emollients and baths), which will be

Product: Secukinumab

Protocol Number: CAIN457AUS05T

Date: 14 July 2018

21

reviewed at each appointment. All subjects who receive at least one dosage will be counted in the ITT population.

Week 16 will be the final endpoint for efficacy assessment of the double-blind phase.

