5.2.2 Double-Blind Phase: Placebo arm

Subjects who meet eligibility criteria and have a normal baseline physical examination and laboratory testing will be enrolled in the double-blind phase. Each subject will receive 300 mg s.c. of placebo using two pre-filled syringes at Baseline (Day 0), Weeks 1, 2, 3, 4, 8 and 12.

Injections will be performed at the site for the initial visit to train subjects in proper subcutaneous injection technique. Subjects will use the second syringe to demonstrate the ability to inject themselves. After this baseline instruction and observation of injection technique, subjects will be able to self-administer weekly or monthly injections.

We will contact subjects weekly by phone/Skype/FaceTime (subject will designate which is best) on weeks 1-3 to answer questions, assess compliance with administration, including proper disinfection of patient's hands and administration site, and ensure safety and return at week 4. Subjects will keep a diary of administration dates and times (as well as use of emollients and baths), which will be reviewed at each appointment. All subjects who receive at least one dosage will be counted in the ITT population.

Week 16 will be the final endpoint for efficacy assessment of the double-blind phase and, at week 16, we will switch placebo-treated patients to secukinumab as all patients enter the open-label phase.

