5.3 Crossover Phase

Because patients and investigators cannot know if they received secukinumab or placebo initially and the subjects who crossover need to receive weekly injections in the first month, all subjects will receive secukinumab 300mg at Week 16, followed by 3 weekly (week 17, 18, 19) administrations (2 syringes) of either placebo (if on secukinumab originally) or secukinumab (if previously on placebo).

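### Weekly adverse-event calls are scheduled only in weeks 1-3, so placebo patients who start secukinumab at week 16 have one scheduled adverse-event query in their first four weeks on drug, against four in the original secukinumab arm

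*Combined protocol and SAP*

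**What the plan says.** Section 6.2.5 sets two routes for scheduled adverse-event questioning. The first is the clinic: "Adverse event assessments will occur at visits 1-12". The second is the telephone: the coordinator asks "about tolerability and any adverse events during the weekly phone or Skype sessions during weeks 1-3 of the study".

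The same calls appear in three treatment sections, always with the same limit:

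- Section 5.2.1 (secukinumab arm): "on weeks 1-3 to answer questions, assess compliance with administration, including proper disinfection of subject's hands and administration site"
- Section 5.2.2 (placebo arm): "on weeks 1-3 to answer questions, assess compliance with administration, including proper disinfection of patient's hands and administration site"
- Section 5.6.2 (general instructions): "on weeks 1-3 to answer questions, assure adherence to administration, and ensure safety and return at week 4"

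At week 16 all subjects receive secukinumab in clinic. Former placebo subjects then take three further weekly loading doses, while former secukinumab subjects take three weekly placebo injections to protect the blind. Section 3.4.3 states: "Weeks 17, 18, and 19 will be administered by the subject (or a caregiver) at home". Section 5.3 gives as part of the reason that "the subjects who crossover need to receive weekly injections in the first month". The next in-person visit is week 20 (Sections 3.4.4 and 5.3.1, Appendix 1). None of these sections mentions a call in weeks 17-19.

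**The concern.** The protocol has a clear pattern for starting treatment: one dose in clinic, three weekly doses at home, and a call in each of the home weeks that covers safety as well as technique. At week 16 the dosing pattern is repeated for every former placebo subject, but the calls are not. For half the randomized subjects, therefore, the weekly calls fall while they inject placebo and none falls while they are first exposed to the drug.

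First exposure is when closer questioning has an obvious purpose. Section 1.6 says "Anaphylaxis and cases of rash or urticaria occurred in secukinumab treated patients in clinical trials", and it also warns that skin infections may be more frequent in this population. A mild reaction or minor infection after a home dose may be forgotten, or reported late, if the next scheduled question is up to four weeks away. Any reader who later sets the first month on secukinumab in the two groups side by side would be comparing periods with different questioning intensity.

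**Working it through.** No sample-size or power figure is involved. The check is a count of scheduled queries against doses.

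**Inputs**
- Calls with an adverse-event question: weeks 1, 2 and 3 (Section 6.2.5, counted from the start of the study).
- Clinic adverse-event assessments: every visit, including week 4 and week 20 (Section 6.2.5, Appendix 1).
- First four secukinumab doses, original secukinumab arm: weeks 0 (clinic), 1, 2, 3 (home) (Section 3.4.2).
- First four secukinumab doses, former placebo arm: weeks 16 (clinic), 17, 18, 19 (home) (Section 3.4.3).
- Visit windows: ±3 days at week 16 and at week 20 (Appendix 1).
- Randomized: 20 per arm, with 16 per arm after the planned 20% dropout (Section 9.5).

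**Scheduled queries after the first secukinumab dose, through the four-week visit**

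| | Original secukinumab arm | Former placebo arm |
|---|---|---|
| Home doses of active drug | 3 | 3 |
| Calls in those weeks | 3 | 0 |
| Clinic query at four weeks | 1 (week 4) | 1 (week 20) |
| Total scheduled queries | 3 + 1 = 4 | 0 + 1 = 1 |

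**Interval with no scheduled query, former placebo arm**
- Nominal: (20 − 16) × 7 = 28 days.
- Shortest with windows: 28 − 3 − 3 = 22 days.
- Longest with windows: 28 + 3 + 3 = 34 days.
- In weeks 0-4 of the original secukinumab arm the nominal interval is 7 days.

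**Active home doses taken within that interval**
- All 20 cross over: 20 × 3 = 60.
- If the full 20% dropout occurs before week 16: 16 × 3 = 48.

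**Could weeks 1-3 mean the first three weeks on secukinumab?** No. Section 6.2.5 counts them from the start of the study, Section 5.2.2 places them in the placebo arm's double-blind phase, and Section 5.6.2 ties them to the return at week 4.

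**How firm is the inference?** It rests on silence: nothing forbids calls in weeks 17-19. Appendix 1 shows clinic visits only and does not list the weeks 1-3 calls either, so its silence adds little. What carries the point is that all four sections describing the calls stop at week 3, and that the two sections describing the crossover add none.

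**The case against.** The strongest reply is that subjects are not out of reach in weeks 17-19. Section 7.1 instructs them to report events throughout. Section 6.3 lets them book an unscheduled visit for a suspected event and gives them contact details at baseline. Week 20 carries an active adverse-event assessment and a diary review (Appendix 1). This stands. A reader might infer that crossover subjects have no contact, that their events are collected only passively, or that their injections go unchecked. The documents do not support any of these: only scheduled outbound contact is missing, week 20 is an active query covering the whole interval, and adherence is checked then from the diary, though retrospectively.

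A second reply is that the calls served mainly to support new self-injectors. By week 17 a subject has had dosing at weeks 0, 1, 2, 3, 4, 8, 12 and 16, three of these at home, and a four-week gap between queries is already normal between weeks 4 and 16 (eight weeks between visits from week 24 to week 48). This stands in part. Technique needs less support by then, but safety is a separate stated purpose of the calls and Section 6.2.5 adds an explicit adverse-event question. The longer gaps elsewhere do not fall in the first weeks on the drug, and self-reporting was equally available in weeks 1-3, when the protocol still added calls.

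A third reply is that no planned analysis is harmed. A reader might infer that the safety results are biased. The documents do not support that. The primary safety endpoint ends at week 16. In weeks 16-20 both original arms follow the same query schedule, so their comparison is not distorted by it. Section 9.4 tabulates weeks 0-16 and weeks 16-52, and nothing plans to compare or pool the first month on drug from the two starts.

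**Conclusion.** The point holds as a gap in monitoring frequency. After first secukinumab exposure, former placebo subjects have 1 scheduled adverse-event query through the four-week visit, against 4 in the original secukinumab arm. The unqueried interval is nominally 28 days (22 to 34 with windows) and covers 48 to 60 active home doses.

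The likely effect is some under-capture of mild, transient events and later site awareness of others. Its size cannot be estimated from the documents. It would matter for inference only if someone made an unplanned comparison or pooling of first-month rates from the two starts.

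This rests on two assumptions: that the protocol's silence means no calls were intended in weeks 17-19, and that between 16 and 20 former placebo subjects reach week 16. It is an inexpensive improvement to safety follow-up, and it does not challenge the primary results.

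**What to change.** In Sections 5.3, 5.6.2 and 6.2.5, extend the existing weekly phone or video contact, with its adverse-event and adherence questions, to weeks 17, 18 and 19. Apply it to all subjects in both arms: both receive blinded weekly injections in those weeks, and calling only one group would reveal the original assignment. Add a row to Appendix 1 showing the contacts in weeks 1-3 and weeks 17-19.

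The cost is at most 40 × 3 = 120 short coordinator calls across two sites, or 32 × 3 = 96 if the planned 20% dropout occurs before week 16. No visit, sample or procedure is added, and no dose or clinical rule changes.
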